conditions shown as "Experimental" (myoelectric control with the liner and ASTERISK system) and "Control" (standard prosthetic device configuration). For the control condition, the subject will be using their everyday prosthesis. For the experimental condition, we will fabricate and provide a new socket to allow for the additional socket volume necessary for liners worn with the ASTERISK electrodes. Each subject will participate in both conditions of the study. The condition that each subject completes first will be chosen by a random number generator that also ensures block randomization with an equal number of participants assigned to each condition first in the test sequence using a custom program that was created under a prior research project.

Subjects will participate in four research visits and will take part in two, one-month long take-home periods. Some researchers have suggested that persons with transradial amputation require, on average, 3–5 weeks of training [22], while others have suggested that 5 hours of training is sufficient [23]. Therefore, we expect a one-month take-home period to be sufficient to allow users to become comfortable with each socket configuration while optimizing the take-home duration to maximize study efficiency.

Twelve subjects will be recruited for this study to allow for a 25% dropout rate and still ensure that we meet our goal of at least 9 subjects to achieve our desired statistical power level (described in the Statistical Plan below). Each subject will use their current prosthetic terminal device (e.g., prosthetic hand) with the experimental socket. If the subject normally uses a wrist rotator prosthesis, then LTI will provide one to be installed in their experimental socket. As described above, the OPUS-SD (survey) will serve as our primary outcome measure for this study, but we will also collect secondary outcome measures, including the Socket Comfort Score (survey), Prosthesis Evaluation Questionnaire (survey), AMULA, prosthetic wear time/usage, and elbow range of motion.

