Participant Eligibility: All subjects must be current wearers of trans-radial myoelectric prostheses or orthoses, have used their prostheses/orthoses for at least six months, be between the ages of 18 and 89 years, understand spoken and written English (for the purpose of consenting), and not have any neurological or physical conditions which would prevent them from performing the experimental tasks. The risks to pregnant people and fetuses are unknown and therefore those who are pregnant should not participate in the study and will be screened by self-disclosure. Subjects in this study will not be discriminated against due to sex/gender or race/ethnicity. Potential subjects will be screened via telephone for eligibility for the study.

STUDY PROTOCOL

Visit 1: During the first visit, the subject will be consented and enrolled in the study. Measurements and casts will be taken so an experimental socket can be fabricated. Subjects will then be asked to complete the in-lab validated outcomes measures (OPUS-SD, PEQ, AMULA, elbow range of motion, SCS, etc.) as described above to provide a baseline measure of function and satisfaction with their usual prosthesis. If there is leftover time and the subject is not fatigued, this battery of tests may be repeated to help to reduce the learning effects associated with performing a new task. By having the subject practice these tests, learning effects will be reduced as they enter into the 2x2 crossover portion of the study. The 2x2 crossover design was specifically chosen to help mitigate the impact of learning effects related to the administration of outcome measures that are new to the test subjects by randomizing the order of conditions. Over the next few weeks following Visit 1, a study prosthetist will create the experimental socket with our ASTERISK system integrated into it. Once the experimental socket is fabricated, the subject will return for Visit 2.

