A power analysis was conducted using the MGH sample size calculator software for cross-over studies [27] to determine the study population needed to reject the null hypothesis that the ASTERISK does not change prosthesis satisfaction as measured by the OPUS-SD. This calculation was performed with the assumptions that we are planning a study of a normally distributed, continuous response variable from a 2x2 cross-over of study subjects. Data described above indicated that the difference in the response of matched pairs is normally distributed with a standard deviation of 12.2. If the true difference in the mean response of the matched pairs is 15 points on the OPUS-SD, the calculation concluded that we would need to study 9 subjects to achieve the standard target of 80% statistical power. From the MGH calculator, with 9 subjects, the probability is 89 percent that the study will detect a treatment difference at a two-sided 0.05 significance level.

Subject Recruitment, Test Sites, and Sub-Populations: To account for potential subject attrition, we will recruit 12 subjects that are current wearers of trans-radial myoelectric prostheses to allow for a 25% dropout rate to ensure that we will reach our goal of 9 subjects completing the study. The 12-subject estimate from this analysis directly aligns with the 12-subject recommendation for pilot studies from Moore et al. [24] described above, and therefore we are confident that our proposed pilot study will allow us to generate valuable information to guide the design of future clinical trials.

Recruitment of more than a modest number of upper limb prosthetics subjects can be difficult. Therefore, planned subject recruitment has been distributed across three test sites: LTI (2 subjects), WPI (6 subjects) and Handspring Clinical Services (4 subjects), and can be redistributed as necessary. While the ASTERISK could have great benefit to users of other amputation levels, this pilot study will focus on transradial users to keep the population as homogeneous and focused as possible.

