In addition to the three experimental sites visited by subjects, three other entities will participate in the project team. [name] (Occupational Therapist; Assistant Professor, Western New England University) will provide occupational therapy on-site to subjects at all experimental sites. [name] (Newton Statistical Consulting) will provide data analysis and statistical consulting for the overall project. Lastly, faculty and staff from Nursing and Health Professions at University of Hartford will also provide prosthesis fabrication for the experimental work occurring at all three sites.

Secondary Measures: As described above, we performed the power analysis based on our principal hypothesis. However, we plan to do much more in depth and rigorous analysis of our 2x2 randomized crossover study data upon completion of data collection. We will also examine several other outcome measures such as elbow range of motion, AMULA scores, SCS scores, PEQ scores, and prosthesis wear time. Again, we recognize that this pilot study may not demonstrate definitive evidence for a treatment effect of the intervention. However, it will allow us to explore models that can be used in future clinical studies. In addition, we hope that the proposed experiments will generate variance data across the battery of additional outcomes measures that can be published to help future researchers plan their clinical studies.

Statistical Model: The primary statistical analysis will be led by [name] and will consist of the development of a generalized liner mixed model (GLMM) for crossover designs. In this 2x2 crossover study, 2 treatments will be administered in 2 periods and 2 sequences, as described above. We will employ a linear mixed model for this design as discussed in multiple references [28,29]. The model will contain

fixed effects for treatment, sequence, and period as well as random effects for subject and test site. Models with and without treatment carryover effects will be examined.

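### Does the crossover credit ASTERISK with a gain that a freshly fitted socket might have produced?

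*Combined protocol and SAP*

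**What the plan says.** The Study Design section defines the two conditions. For the new device: "For the experimental condition, we will fabricate and provide a new socket to allow for the additional socket volume necessary for liners", to be worn with the ASTERISK electrodes. For the comparator: "For the control condition, the subject will be using their everyday prosthesis". The Visit 1 text adds: "Measurements and casts will be taken so an experimental socket can be fabricated".

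Some parts are held constant. "Each subject will use their current prosthetic terminal device (e.g., prosthetic hand) with the experimental socket". If a subject normally uses a wrist rotator, "then LTI will provide one to be installed in their experimental socket".

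Under Statistical Model, the analysis has "fixed effects for treatment, sequence, and period as well as random effects for subject and test site", so there is a single treatment term. Under Power Analysis, the sample size is chosen to "reject the null hypothesis that the ASTERISK does not change prosthesis satisfaction as measured by the OPUS-SD". Participant Eligibility requires that subjects "have used their prostheses/orthoses for at least six months". This is a minimum duration of use and says nothing about the age of the current socket.

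The comparison is worded more fully elsewhere. The primary hypothesis in the introduction sets a liner with the wireless electrodes against the standard myoelectric prosthesis. The secondary hypothesis on function describes the two test conditions as two socket configurations. The principal hypothesis that opens Power Analysis names standard socket configurations as the comparator.

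**The concern.** Three things change together when a subject moves to the experimental condition: a newly cast socket, a liner, and wireless electrodes with their receiver. The extra volume and the lower trimlines belong to the treatment, because the liner and electrodes need or permit them. The fresh cast and fit is different. A conventional socket could also be remade, and the text neither limits nor records the age of the everyday socket.

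The plan chose OPUS-SD because it covers fit, comfort and skin health, and it describes the Socket Comfort Score as sensitive to changes in fit. A fresh fit could therefore act directly on the primary outcome. Read literally, rejecting a null that names only ASTERISK would credit the electrodes with a difference that belongs to the whole package. The pilot's means and variances are also meant to prepare a later trial of the ASTERISK system, so a wrong attribution could be carried forward.

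**Working it through.** **1. The plan's own figures.** Inputs from Power Analysis: difference 15 points, SD of the within-subject difference 12.2, two-sided 0.05, 9 completers.

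- Noncentrality = (15 / 12.2) × √9 = 3.69.
- Power by noncentral t: 88.4% with 7 degrees of freedom (crossover), 89.6% with 8 (paired). The plan states 89%.
- Recruitment: 9 / (1 − 0.25) = 12, as stated.

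The concern disturbs none of these.

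**2. What the design can estimate.** Twelve subjects in two periods give 24 observations in four sequence-by-period cells.

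- Intercept, sequence, period and one treatment column: rank 4 of 4.
- The treatment column replaced by separate columns for new socket, liner and ASTERISK: the three are identical (pairwise correlation 1.00), so the rank stays at 4 while the columns rise to 6.
- With subjects as fixed effects: rank 14 of 14 against 14 of 16.

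This is the version without carryover. Adding a carryover column does not help, because four cells cannot support a rank above 4. One contrast, configuration against configuration, is estimable, and its components are not.

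**3. Whether that contrast is soundly tested.** Half-width of the 95% interval = t × 12.2/√n, with n − 2 degrees of freedom.

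- n = 9: 2.365 × 4.067 = 9.62 points.
- n = 12: 2.228 × 3.522 = 7.85 points.

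Both are below the 15-point target. They depend only on the total difference, however it divides between fit, liner and electrodes. They describe a valid test and measure no error.

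**4. The null read in place.** It follows, within the same Power Analysis, a principal hypothesis that names standard socket configurations as comparator, and its own paragraph specifies a 2×2 crossover with matched pairs. The text for Visits 1 and 2 describes the ASTERISK system as built into the experimental socket. In this setting the device name stands for the experimental condition.

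**5. What the possible remedies would change.**

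- *Rewording the null as a contrast of configurations.* The model, the estimate and the sample size stay the same.
- *Recording the age of the everyday socket.* A correlation with the OPUS-SD difference reaches significance only above t/√(t² + n − 2). This is 2.365/√(5.593 + 7) = 0.67 with 9 subjects and 2.228/√(4.964 + 10) = 0.58 with 12. Such a listing could not show where a gain came from. Comfort and satisfaction with the everyday socket are already measured at Visits 1 and 2.
- *Labelling the estimates as package estimates.* Under Pilot Validation Study the pilot is meant to mirror the later trial, and for a trial of the same package the estimates already suit.
- *A newly made conventional socket as control.* This would isolate the fresh fit, but it needs a second socket for each of 12 subjects and would replace the planned comparison with the prosthesis that the subject actually uses.

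**The case for a change.** The strongest case for a change is that the formal null is the sentence a reader takes as the claim, and it names one component of three. The unnamed component acts on exactly what OPUS-SD and the Socket Comfort Score measure. No sentence in the plan says that the component effects are not isolated, and the introduction attributes the expected benefit to liners. Calling the study a pilot lowers the stakes but does not address attribution. If the name is shorthand, one sentence would define it.

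The factual part stands: the components are inseparable, and an explicit caveat is absent. Two parts do not stand. The null does not lack a comparator once it is read with the paragraph before it. And the risk to the later trial arises only if that trial changes the socket comparison, which the documents do not propose. What remains is a preference for fuller wording.

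**Conclusion.** No change follows. The trial estimates the difference between a configuration (new socket, liner, ASTERISK electrodes) and the everyday prosthesis, and the plan largely says so. The single-name null is a clerical shorthand. Using the everyday prosthesis as control is a fair trade-off in a 12-subject pilot, which the plan says may not give definitive evidence of a treatment effect.

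The effect on the planned result is nil: the same model, the same 9 completers from 12 recruits, and the same power of about 88% to 90%. A bias from fresh fit cannot be sized, because the documents give no figure or direction for it.

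The conclusion assumes that the report describes the result as a difference between configurations, as the hypotheses do, and that the follow-on trial keeps the same package. A sentence saying that socket, liner and electrode effects are not separated would be a harmless courtesy to readers, but the analysis does not depend on it.

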One-Month At-Home (Condition A): Subjects will be asked to wear their experimental prosthesis and perform their daily activities either using their everyday socket (control condition) or socket with liner and ASTERISK sensors (experimental condition). An ActiGraph activity monitor (worn like a wristwatch; provided by the experimenters for use by the subjects) will be worn on the prosthesis to monitor prosthesis usage throughout the day. The ActiGraph contains an inertial measurement unit that records prosthetic lime acceleration, rotation and orientation. It does *not* record a subject's location. All subjects will be asked to keep a daily log to track any issues they have with their prosthesis and help identify and document any issues with real-world use of the device. Researchers will periodically check-in with the subject (by phone, text, email, etc.) to maximize adherence to the daily log, debug any technical issues, etc.

Visit 3: After one month, subjects will return for Visit 3. At this time the data will be downloaded from the ActiGraph monitor and the daily log collected. Subjects will perform the same in-lab testing as in Visits 1 & 2, with subjects performing the functional outcomes measures using the prosthetic control modality used in the prior month and providing feedback on the system via a custom survey developed as part of this effort. The test conditions will then be switched (those using the control condition in the first month will now use the experimental condition and vice versa) and subjects will receive training on the second test condition. For those switching to the experimental condition, instructions will be given on the use of the ASTERISK sensors. All subjects will be instructed and trained on their newly assigned prosthesis control condition by a study OT as described in Visit 2. Once trained, subjects will again be sent home to use the device in a real-world environment.

One-Month At-Home (Condition B): This is the same as the first one-month take-home session, except subjects have swapped conditions. All subjects will once again be asked to keep a daily log to track any technical issues. Researchers will periodically check-in with the subject to maximize adherence to the daily log, debug any technical difficulties, etc.

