With 6 subjects in each treatment sequence group, the model, without covariates, is as follows: $y_{ijk} = \mu + \alpha_i + \beta_k + \tau_d + \lambda_c + d_{ij} + e_{ijk}$, where: $i, k, d, c = 1, 2; j = 1, 2, ..., 6; y_{ijk}$ is the response of the j^{th} subject in the i^{th} sequence and the k^{th} period; μ is the general mean; α_i is the sequence effect; β_k is the period effect; τ_d is the direct treatment effect; λ_c is the carryover effect (0 for period 1); d_{ij} is the random effect associated with the j^{th} subject in the i^{th} treatment sequence; and e_{ijk} is random error associated with the j^{th} subject in sequence i at period k. Additional terms in the model will include a random effect for test site (as testing will occur at LTI, WPI, U. Hartford and Handspring Clinical Services) to increase precision of the estimates. In a 2x2 crossover design, carryover effects are confounded with the other effects. We will examine models omitting each of the effects in turn to assess their contribution and we will consider the inclusion of a washout period between test conditions to better characterize these effects when finalizing the study design.

Statistical Analysis: Prior to fitting models, exploratory data analysis, including numerical and graphical summaries, will be conducted to examine distributions and check for outliers. In addition, plots will allow visual assessment of relationships between predictors and outcome. The fitted models also will be assessed by graphical and numerical means. Residuals will be examined for conformance to model assumptions. It is possible that transformation of some of the response variables may be necessary. Additionally, we will provide appropriate corrections for any sets of multiple comparisons during post-hoc analyses (e.g., Bonferroni-Holm) as required. We will work with our statistician, [name], to design the study to get as much useful data out of a relatively small number of subjects as possible.

REFERENCES (Those used in this "protocol" and as numbered from the original grant application.)

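### The displayed crossover equation includes carryover, so it cannot estimate the treatment effect, and no model is named as the primary OPUS-SD test

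*Combined protocol and SAP*

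**What the plan says.** All references are to the combined protocol and SAP.

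- **Statistical Model, term list.** The primary analysis is described as building a mixed model with "fixed effects for treatment, sequence, and period as well as random effects for subject and test site". Carryover is not in this list. The next sentence adds: "Models with and without treatment carryover effects will be examined".
- **Statistical Model, equation.** The text continues "With 6 subjects in each treatment sequence group, the model, without covariates, is as follows". The equation has a general mean, sequence, period, direct treatment, carryover (zero in Period 1), random subject and error. A random site effect is to be added.
- **After the equation.** The plan concedes: "In a 2x2 crossover design, carryover effects are confounded with the other effects". Its stated response is to fit reduced models: "We will examine models omitting each of the effects in turn to assess their contribution". On washout it commits only this far: "we will consider the inclusion of a washout period between test conditions".
- **Study Protocol, Visit 3.** "The test conditions will then be switched". The schedule as written has no washout.
- **Power Analysis.** For a 15-point OPUS-SD difference, an SD of the within-subject difference of 12.2 and 9 subjects, "the probability is 89 percent that the study will detect a treatment difference at a two-sided 0.05 significance level".

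OPUS-SD is named as the primary outcome and its improvement as the principal hypothesis. No sentence links that hypothesis to one of the models.

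**The concern.** A 2x2 crossover measured once per period yields four cell means. The displayed equation puts five fixed parameters on them, so it has no unique treatment effect. Software given this equation will either drop a term or return a value that depends on its coding.

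The plan's wish to examine models with and without carryover, and to omit effects in turn, does not settle the matter. Different omissions lead to different treatment estimates, or to none. At stake is whether the one powered test in the plan is a within-subject comparison, a between-subject comparison in Period 1, or undefined.

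**Working it through.** **Inputs.** Effect 15 points, SD of the within-subject difference 12.2, two-sided alpha 0.05, 9 completers out of 12 recruited (all from Power Analysis and the recruitment paragraph). The within-subject correlation ρ is not in the plan and is my assumption.

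**1. The plan's own figure.** Paired t, df 8: noncentrality 15/(12.2/√9) = 3.69, power 89.6%. Crossover analysis with a period effect, split 5/4, df 7: SE = (12.2/2)·√(1/5 + 1/4) = 4.09, noncentrality 15/4.09 = 3.67, power 88.0%. Both agree with the stated 89% to within about a point, so that figure belongs to the within-subject comparison without carryover.

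**2. Estimability of the displayed equation.** Order the cells as sequence 1 Period 1, sequence 1 Period 2, sequence 2 Period 1, sequence 2 Period 2. The contrast columns are:

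- sequence: (1, 1, −1, −1)
- period: (1, −1, 1, −1)
- treatment: (1, −1, −1, 1)
- carryover: (0, 1, 0, −1)

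Carryover = (sequence − treatment)/2 exactly. With the mean there are five columns of rank 4, and treatment is not estimable. Giving the two treatments separate carryover parameters makes six columns, still of rank 4. Random subject and site effects do not alter the aliasing.

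*Illustration.* Cell means 77.5, 62.5, 62.5, 77.5 fit exactly with treatment +15 and no carryover. They fit equally well with treatment 0, sequence +15 and carryover −30: with a mean of 70, sequence 1 gives 77.5 then 77.5 − 15 = 62.5, and sequence 2 gives 62.5 then 62.5 + 15 = 77.5.

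**3. Omitting effects in turn.**

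| Starting model | Omitted | Rank / parameters | Treatment weights on the four cells |
|---|---|---|---|
| Displayed equation | carryover | 4 / 4 | 0.5, −0.5, −0.5, 0.5 (within-subject) |
| Displayed equation | sequence | 4 / 4 | 1, 0, −1, 0 (Period 1 only) |
| Displayed equation | period | 3 / 4 | not estimable |
| Term list without carryover | nothing, sequence or period | full | 0.5, −0.5, −0.5, 0.5 each time (complete data) |

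A washout without a new measurement adds no cell, so the displayed equation would stay at rank 4.

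**4. Power for 15 points.** Within-subject model: as in step 1 for 9 completers. For 12 (6/6, df 10), SE = 6.1·√(1/6 + 1/6) = 3.52. Half-widths of the 95% CI are 2.365 × 4.09 = 9.7 and 2.228 × 3.52 = 7.8 points.

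Period 1 only: single-measurement SD = 12.2/√(2(1 − ρ)), assuming equal variances in the two periods, and SE = SD·√(1/n₁ + 1/n₂).

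| Analysis | 9 completers (5/4) | 12 completers (6/6) |
|---|---|---|
| Within-subject, no carryover | 88% | 97% |
| Period 1 only, ρ = 0.5 (SD 12.2; SE 8.18, 7.04) | 35% | 49% |
| Period 1 only, ρ = 0.8 (SD 19.3; SE 12.94, 11.14) | 17% | 23% |
| Period 1 only, ρ from 0 to 0.9 | 61% to 11% | 77% to 14% |

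The Period 1 rows use a two-sample t test. A mixed model that pools variance over both periods does slightly better in simulation: 39% to 18% with 9 completers and 51% to 24% with 12, for ρ from 0.5 to 0.8 and site omitted.

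**5. Price of leaving carryover out.** If carryover differs by L points between treatments, its column is (0, L/2, 0, −L/2). Applying the within-subject weights gives −L/4 − L/4 = −L/2. For L = 5, a true 15 is estimated on average as 12.5. Power falls from 88% to 75% with 9 completers and from 97% to 89% with 12.

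**The case against.** The plan goes some way to handling this. Its term list is estimable and appears in the paragraph on the primary analysis. OPUS-SD is the declared primary outcome, so a sympathetic reader would join the two. The confounding is admitted just after the equation, which may be meant only as full notation from which reduced models are drawn. Effects are to be omitted to judge their contribution, not to choose the primary test, so the Period 1 analysis is an unlikely route to the reported result. The correlation range is assumed. Modelling the Visit 2 baseline as a third response could make treatment estimable with carryover kept, if the sequence effect is common to all occasions. The study is also a pilot that disclaims definitive evidence.

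Much of this stands, and it limits the weight of the point. The low-power figures are conditional, and the pilot's variance and feasibility aims are untouched. But the plan does not specify the three-occasion model. None of these arguments makes the displayed equation estimable, and none supplies the missing statement of which model decides the OPUS-SD test. The plan also wants its models to serve later trials, so the equation could be carried forward.

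**Conclusion.** The concern holds and should be fixed. That treatment cannot be estimated from the displayed equation is exact algebra and does not depend on sample size. The equation also disagrees with the plan's own term list, and neither is tied to the powered OPUS-SD test.

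Under the carryover-free model, the sample size and the stated 89% need no change. The loss of power applies only if carryover is kept, sequence is dropped and that fit is used as the test. Its size depends on a correlation that the plan does not give.

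**What to change.** 1. Remove the carryover term from the primary equation so that it matches the term list.
2. State that the treatment contrast from that model, using OPUS-SD at Visits 3 and 4, is the single primary test at two-sided 0.05.
3. State that the models with carryover and those omitting one effect are exploratory and neither select nor replace the primary analysis.
4. Optionally, add one labelled carryover sensitivity analysis: the Visit 3 comparison between sequences, adjusted for the Visit 2 baseline already collected. Note its low power for 15 points: by simulation about 38% to 33% with 9 completers and 55% to 48% with 12, for ρ from 0.5 to 0.8.

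The cost is SAP wording, with no new data or visits. The drawback is that the primary analysis then openly assumes no differential carryover, with the bias of −L/2 shown above if that assumption fails.
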